7.1.1.3 Medical History

A medical history will be obtained by the investigator or qualified designee. Medical history will include all active conditions, and any condition diagnosed within the prior 10 years that are considered to be clinically significant by the Investigator. Details regarding the disease for which the subject has enrolled in this study will be recorded separately and not listed as medical history.

7.1.1.4 Prior and Concomitant Medications Review

7.1.1.4.1 Prior Medications

The investigator or qualified designee will review prior medication use, including any protocol-specified washout requirement, and record prior medication taken by the subject within 28 days before starting the trial. Treatment for the disease for which the subject has enrolled in this study will be recorded separately and not listed as a prior medication.

7.1.1.4.2 Concomitant Medications

The investigator or qualified designee will record medication, if any, taken by the subject during the trial. All medications related to reportable SAEs and ECIs should be recorded as defined in Section 7.2.

7.1.1.5 Disease Details and Treatments

7.1.1.5.1 Disease Details

The investigator or qualified designee will obtain prior and current details regarding disease status. These may be recorded at screening for some aspects (e.g. sites of disease). This will include the following:

- Prior treatments including response
- Date of diagnosis of primary tumor and advanced disease
- Sites of organ involvement

7.1.1.5.2 Prior Treatment Details

The investigator or qualified designee will review all prior cancer treatments including systemic treatments, radiation and surgeries.

7.1.1.5.3 Subsequent Anti-Cancer Therapy Status

The investigator or qualified designee will review all new anti-neoplastic therapy initiated after the last dose of trial treatment. If a subject initiates a new anti-cancer therapy within 30 days after the last dose of trial treatment, the 30 day Safety Follow-up visit must occur before the first dose of the new therapy. Once new anti-cancer therapy has been initiated the subject will move into survival follow-up.

7.1.1.6 Trial Compliance (Medication/Diet/Activity/Other)

A representative from the coordinating institution will review records to ensure compliance. Data will be collected via CRFs and entered into the database per Sponsor guidelines. The Sponsor will check data accuracy by performing source data verification. Source data verification is a direct comparison of the entries made on the CRFs against the appropriate source documentation. Discrepancies in the data will be brought to the attention of the Investigator and/or the Investigator's staff. Any necessary corrections will be made directly to the CRFs or via queries by the Investigator and/or the Investigator's staff.

7.1.2 Clinical Procedures/Assessments

7.1.2.1 Adverse Event (AE) Monitoring

The investigator or qualified designee will assess each subject to evaluate for potential new or worsening AEs as specified in the Trial Flow Chart and more frequently if clinically indicated. Adverse experiences will be graded and recorded throughout the study and during the follow-up period according to NCI CTCAE Version 4.0 (see Section 12.2). Toxicities will be characterized in terms regarding seriousness, causality, toxicity grading, and action taken with regard to trial treatment.

All AEs of unknown etiology associated with pembrolizumab exposure should be evaluated to determine if it is possibly an event of clinical interest (ECI) of a potentially immunologic etiology (irAE). See Section 5.6.1.1 and the separate guidance document in the administrative binder regarding the identification, evaluation and management of AEs of a potential immunological etiology.

Please refer to section 7.2 for detailed information regarding the assessment and recording of AEs.

7.1.2.2 Physical and Ophthalmologic Exam

The investigator or qualified designee will perform a complete physical exam during the screening period. Clinically significant abnormal findings should be recorded as medical history. A full physical exam should be performed during screening,

For cycles that do not require a full physical exam per the Trial Flow Chart, the investigator or qualified designee will perform a directed physical exam as clinically indicated prior to trial treatment administration.

Subjects may have an optional standard ophthalmic examination performed by an ophthalmologist at the times described (Section 6) to assess changes in any residual primary tumor (including treated tumors). At certain time points in the trial and if visual changes develop, an eye exam is indicated. The exam will include best corrected visual acuity, color vision (Ishihara color plates), measurement of tear production with Shirmer's strips, tonometry, slit lamp biomicroscopic examination, and dilated indirect fundoscopy with special attention to retinal abnormalities. Fundus photography of both maculas and optic discs, and of the tumor, should be obtained at all visits. Optical coherencetomography is strongly recommended at scheduled visits, and if retinal abnormalities are suspected. Other types of ancillary testing including fluorescein angiography are also recommended if clinically indicated. B scan ultrasonographic measurements of residual tumor height should be obtained at baseline and at follow-up visits. All adverse events should be graded and documented separately for the tumor and for the non-tumor eye. See Appendix 13.5 for Ophthalmology Documentation Form.

7.1.2.3 Vital Signs

The investigator or qualified designee will take vital signs at screening, prior to the administration of each dose of trial treatment and at treatment discontinuation as specified in the Trial Flow Chart (Section 6.0). Vital signs should include temperature, pulse, respiratory rate, weight and blood pressure. Height will be measured at screening only.

7.1.2.4 Eastern Cooperative Oncology Group (ECOG) Performance Scale

The investigator or qualified designee will assess ECOG status (see Section 12.4) at screening, prior to the administration of each dose of trial treatment and discontinuation of trial treatment as specified in the Trial Flow Chart. After Cycle 8 assessment of ECOG status will be performed every other cycle in conjunction with the directed or full physical exam.

7.1.2.5 Eligibility for Second Course of Treatment

Patients who discontinue pembrolizumab with a CR prior to 24 months or with best response of PR or SD may be eligible for a second course of pembrolizumab therapy. Prior to enrollment in a second course, screening tests are required as outlined in section 6.2. Subjects will receive pembrolizumab 200mg IV q3 weeks for up to 12 months. All other on-treatment procedures are the same as in the initial phase and are outlined in section 6.2. Subjects are eligible for retreatment if they meet the following criteria:

- Best response of CR, PR, or SD
- Treatment for 12 months or more if confirmed CR, PR, or SD
- Subsequent progression of disease as defined by irRECIST criteria
- If immune related adverse events occurred on the initial course, they must have not caused treatment discontinuation and must be resolved at the time of consideration
- ECOG performance status of 0-1
- No intervening systemic therapies following initial course of pembrolizumab
- Other inclusion criteria as outlined in section 5.1.2 and 5.1.3.

If extenuating circumstances occur, discussion with the PI can occur and consideration will be given to retreatment.

7.1.2.6 Tumor Tissue and Blood Collection

Collection of tumor tissue is required prior to enrollment in this study to evaluate an important potential biomarker, PD-L1 that may be predictive of treatment benefit from pembrolizumab. A newly obtained tumor biopsy is highly desirable and preferred, but an

archival tumor specimen is acceptable if a new biopsy cannot be obtained. Patients should submit the specimen for central pathology assessment of PD-L1 status. The results of PD-L1 status are not required to initiate pembrolizumab.

Patients who submit an inadequate archival sample may undergo new biopsy and patients who submit an inadequate recent biopsy may undergo a rebiopsy at the discretion of the investigator. Fine needle aspirations are not acceptable specimens. If a patient is unable to provide a newly obtained tumor biopsy, then collection of archival tumor tissue is required. If a patient has multiple archival tumor tissue samples, the most recently obtained tissue sample is preferred. Finally, if an acceptable archival sample or new biopsy specimen is unable to be obtained due to safety reasons, the requirement may be waived and a patient may be enrolled.

If a patient is unable to provide an archival tissue sample, then collection of a newly obtained tumor biopsy is highly encouraged. Tru-cut (or equivalent) core needle biopsies and surgical biopsies are acceptable. Fine needle aspirations are not acceptable. In addition, tumor biopsies while on study therapy at approximately Week 6, Week 12, and Week 24 and at disease progression are also desirable, especially in patients who initially responded but then progressed on pembrolizumab as changes in biomarkers compared to baseline may provide meaningful insights into characteristics associated with sensitivity or resistance to pembrolizumab.

In addition, at the discretion of the investigator, new lesions or fluid collections may require histological or cytological confirmation if progression is suspected, if indicated by the clinical circumstances. If a new lesion or fluid collection is biopsied during the course of the study to document progressive disease or evaluate suspicious new findings, the date of the procedure, type of procedure, and the histological or cytological results of the biopsy should be recorded in the case report forms.

Assessment of peripheral blood lymphocyte profiles may also yield critical insights into response and resistance to pembrolizumab. Blood collection is required on day 1 of pembrolizumab treatment, two weeks into treatment (cycle 2), and at the time of progression. Twenty (20) ml of peripheral blood should be obtained at each timepoint.

7.1.3 Tumor Imaging and Assessment of Disease

The Immune Related RECIST (irRECIST) will be used for assessment of tumor response for the purposes of managing patients on protocol treatment and decision making for discontinuation of study therapy due to disease progression. These disease assessments will be performed by the investigator with site radiology reading. At least one measurable lesion according to RECIST 1.1 criteria must be present on a bi-dimensional imaging study (CT or MRI) at baseline. A measurable lesion is defined as measuring at least 10 mm in longest diameter or twice the slice thickness whichever is greater; the exception being that lymph nodes must measure 15 mm in short axis for lymph nodes.

The irRECIST criteria are described in Section 7.1.3.3. For the purposes of the efficacy endpoints of the study, response assessment based on irRECIST will be applied as the primary measure.

If imaging shows a complete response (CR) or partial response (PR), tumor imaging should be repeated at least 4 weeks later to confirm response, per irRECIST recommendations. Patients will then return to regular scheduled imaging, starting with the next scheduled imaging time point. Patients who obtain a confirmation scan do not need to undergo scheduled imaging assessment 2 weeks later (e.g. If a patient obtains a scan at Week 16 to confirm a Week 12 response, they will not also be required to complete the scheduled Week 18 scan).

If imaging shows PD, it is at the discretion of the investigator to keep a patient on study treatment or to stop study treatment until imaging is repeated approximately 4 weeks later in order to confirm PD, as described in the irRECIST recommendations. Patients that are deemed clinically unstable or who have biopsy proven new metastatic lesions are not required to have repeat imaging for confirmation. This decision will be based on clinical judgment of a patient's overall clinical condition, including performance status, clinical symptoms, and laboratory data. At a minimum, patients must meet the following criteria for continued treatment on study after disease progression is identified at a tumor assessment:

- Absence of symptoms and signs (including worsening of laboratory values) indicating disease progression
- No decline in ECOG performance status
- Absence of rapid progression of disease or of progressive tumor at critical anatomical sites (e.g., cord compression) requiring urgent alternative medical intervention.

If repeat imaging shows an objective response or stable disease relative to baseline, treatment with pembrolizumab will continue/resume and the next imaging studies will be conducted every 6 weeks as previously scheduled. If repeat imaging confirms PD, patients will be discontinued from study therapy.

In patients who discontinue study therapy early without documented disease progression, every effort should be made to continue monitoring their disease status by radiologic imaging following the guidelines described in Section 7.1.6.4.

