5.8 Subject Withdrawal/Discontinuation Criteria

Subjects may withdraw consent at any time for any reason or be dropped from the trial at the discretion of the investigator should any untoward effect occur. In addition, a subject may be withdrawn by the investigator or the Sponsor if enrollment into the trial is inappropriate, the trial plan is violated, or for administrative and/or other safety reasons. Specific details regarding discontinuation or withdrawal are provided in Section 7.1.4 – Other Procedures.

A subject must be discontinued from the trial for any of the following reasons:

- The subject or legal representative (such as a parent or legal guardian) withdraws consent.
- Confirmed radiographic disease progression

Note: For unconfirmed radiographic disease progression in the absence of clinical deterioration, patients may continue on study.

- Unacceptable adverse experiences as described in Section 5.2.1.2
- Intercurrent illness that prevents further administration of treatment
- Investigator's decision to withdraw the subject
- The subject has a confirmed positive serum pregnancy test
- Noncompliance with trial treatment or procedure requirements
- The subject is lost to follow-up
- Completed 24 months of treatment with pembrolizumab

Note: 24 months of study medication is calculated from the date of first dose. Subjects who stop pembrolizumab after 24 months may be eligible for up to one year of additional study treatment if they progress after stopping study treatment provided they meet the requirements detailed in Section 7.1.2.6.

- Administrative reasons

The End of Treatment and Follow-up visit procedures are listed in Section 6 (Protocol Flow Chart) and Section 7.1.5 (Visit Requirements). After the end of treatment, each subject will be followed for 30 days for adverse event monitoring (serious adverse events will be collected for 90 days after the end of treatment as described in Section 7.2.3.1). Subjects who discontinue for reasons other than progressive disease will have post-treatment follow-up for disease status until disease progression, initiating a non-study cancer treatment, withdrawing consent or becoming lost to follow-up. After documented disease progression

each subject will be followed by telephone for overall survival until death, withdrawal of consent, or the end of the study, whichever occurs first.

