7.1.3.3 Response Criteria (irRC)

7.1.3.3.1 Immune-related RECIST Criteria (irRECIST) Overview

- All measurements are undimensional
- If a patient is classified as having progressive disease, confirmation by a second scan at least 4 weeks later in the absence of rapid clinical deterioration is required to assess for a late response.
- The presence of new lesions does not constitute disease progression by itself.
- Target lesions and new lesions are incorporated into overall tumor burden which is used to evaluate progression or responses as in the following:

Tumor Burden = Sum of the Diameter (target) + Sum of the Diameter (new)

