7.1.3.3.2 Target Lesions

- Up to 5 lesions may be selected as target lesions (up to 2 per organ).
- Immune-related Complete Response (irCR): Disappearance of all target lesions. Any pathological lymph nodes must be < 10 mm in the short axis.
- Immune-related Partial Response (irPR): At least a 30% decrease in the total tumor burden, including target lesions and new lesions, taking as a reference, the baseline sum of the diameters (e.g. percent change from baseline).

- Immune-related Stable Disease (irSD): Neither sufficient shrinkage to qualify for PR nor sufficient increase to qualify for progressive disease.
- Immune-related Progressive Disease (irPD): At least a 20% increase in the tumor burden (defined as the sum of diameters of target lesions and new lesions), taking as a reference, the smallest sum of diameters recorded since the treatment started (e.g. percent change from nadir, where nadir is defined as the smallest sum of diameters recorded since treatment start). In addition, the sum must have an absolute increase from nadir of 5mm.
- Not Applicable (NA): No target lesions at baseline.
- Not Evaluable (NE): Cannot be classified by one of the five preceding definitions.

NOTE:

- If lymph nodes are documented as target lesions the short axis is added into the sum of the diameters (e.g. sum of diameters is the sum of the longest diameters for non-nodal lesions and the short axis for nodal lesions). When lymph nodes decrease to non-pathological size (short axis <10mm) they should still have a measurement reported in order not to overstate progression.
- If at a given assessment time point all target lesions identified at baseline are not assessed, sum of the diameters cannot be calculated for purposes of assessing CR, PR, or SD, or for use as the nadir for future assessments. However, the sum of the diameters of the assessed lesions and the percent change from nadir should be calculated to ensure that progression has not been documented. If an assessment of PD cannot be made, the response assessment should be NE.
- All lesions (nodal and non-nodal) should have their measurements recorded even when very small (e.g., 2 mm). If lesions are present but too small to measure, 5 mm should be recorded and should contribute to the sum of the diameters, unless it is likely that the lesion has disappeared in which case 0 mm should be reported.

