9.2.2.2.3 Duration of Response

If sample size permits, response duration will be summarized descriptively using Kaplan-Meier medians and quartiles. Only the subset of patients who show a complete response or partial response will be included in this analysis.

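### After a first PD, section 7.1.3 judges the repeat scan against baseline for continuing but confirms irPD from nadir for stopping, so one scan can meet both instructions; section 9.2.2.2.3 does not say when a response ends

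*Combined protocol and SAP*

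**What the plan says.** Section 7.1.3 gives two adjacent instructions for the scan that repeats a first PD. The first is "If repeat imaging shows an objective response or stable disease relative to baseline, treatment with pembrolizumab will continue/resume". The second is "If repeat imaging confirms PD, patients will be discontinued from study therapy". Neither refers to the other.

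The categories are defined in three places:

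- **Section 7.1.3.3.2, definitions.** irPD is a rise of at least 20%, "taking as a reference, the smallest sum of diameters recorded since the treatment started", plus an absolute rise of 5 mm from nadir. irSD is residual: neither PR nor PD.
- **Section 7.1.3.3.2, reappearing lesions.** After irCR, reappearance is irPD. After irPR or irSD, both the change from baseline and the change from nadir are used, without ranking.
- **Table 8 (section 7.1.3.3.5).** irPR and irSD are measured against baseline, with irSD running up to a 20% increase over baseline. irPD is measured against either nadir or baseline.

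Section 5.8 lists "Confirmed radiographic disease progression" among the reasons for mandatory discontinuation, and section 5.2.3 also lists it. A note under Table 8 allows an exception after discussion with the PI.

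On timing, section 7.1.3 leaves the decision open "until imaging is repeated approximately 4 weeks later in order to confirm PD". Section 7.1.3.3.1 requires "confirmation by a second scan at least 4 weeks later", and Table 8 and footnote 12 of the section 6.1 flow chart set the same minimum.

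On analysis, section 9.2.2.2.3 says that "response duration will be summarized descriptively using Kaplan-Meier medians and quartiles", for patients with CR or PR, if sample size permits. It gives no end event, event date, criteria set or censoring rule. Section 9.2.2.2.1 bases the main PFS on the first RECIST 1.1 PD and adds a PFS by irRC.

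**The concern.** A responder's nadir lies at or below 70% of baseline. When the tumour regrows, the sum can pass the nadir-based PD threshold well before it exceeds the baseline-based limit for stable disease. In between, one repeat scan satisfies the instruction to continue and the instruction to stop, and two sites could each follow the text and act differently.

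The patients most exposed are responders, who are the whole population of the duration-of-response summary. The irRC-based PFS depends on the same category. So can stable disease in a patient whose nadir lies below baseline, which bears on the provision in sections 2.2.1, 9.1, 9.2.1 and 9.2.2.1 that 24 weeks of stable disease in two patients can open stage 2.

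**Working it through.** The plan states no figure on this point, so the check applies its own thresholds.

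**Inputs.** B is the baseline sum, N the nadir and S the sum at the repeat scan; the first PD scan has already met irPD.

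- irPD (7.1.3.3.2): S ≥ 1.2N and S ≥ N + 5 mm, so S ≥ max(1.2N, N + 5).
- irPR (Table 8): S ≤ 0.7B.
- irSD (Table 8): 0.7B < S < 1.2B.

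**Both instructions apply when** max(1.2N, N + 5) ≤ S < 1.2B.

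| B (mm) | N (mm) | irPD from (mm) | Conflict band (mm) |
|---|---|---|---|
| 100 | 70 | max(84, 75) = 84 | 84 to <120 |
| 100 | 50 | max(60, 55) = 60 | 60 to <120 |
| 100 | 40 | max(48, 45) = 48 | 48 to <120 |
| 20 | 14 | max(16.8, 19) = 19 | 19 to <24 |
| 10 | 7 | max(8.4, 12) = 12 | none (1.2B = 12) |

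The 5 mm floor sets the lower limit whenever N is below 25 mm, because then N + 5 > 1.2N.

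**Worked cases, B = 100 mm.**

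- N = 40, first PD scan 60, repeat scan 62. From nadir: 62/40 − 1 = +55% and +22 mm, so irPD is confirmed. From baseline: 62/100 − 1 = −38%, so still an objective response.
- N = 60, repeat scan 78. From nadir: +30% and +18 mm (irPD). From baseline: −22% (irSD in Table 8).
- A patient with stable disease, N = 85, scan 105. From nadir: 105/85 − 1 = +23.5% and +20 mm (irPD). From baseline: +5% (irSD in Table 8).

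**If irSD is read as residual to irPD,** as in section 7.1.3.3.2, only the irPR/irPD overlap remains. It needs max(1.2N, N + 5) ≤ 0.7B, that is N ≤ 0.7B/1.2 = 0.583B and N + 5 ≤ 0.7B. For B = 100 mm the band is then 60 to 70 mm at N = 50 and 48 to 70 mm at N = 40, and it is empty at N = 60 (72 > 70) and at N = 70.

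**Effect on duration of response (assumed course).** Baseline 100 mm; week 12, 40; response confirmed week 16; week 24, 55; week 28, 55; week 36, 75; week 48, 125. Counting from week 12:

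- ending at the first nadir-based irPD (week 24, 55/40 = +37.5%): 24 − 12 = 12 weeks;
- ending when PR against baseline is lost (week 36, −25%): 36 − 12 = 24 weeks;
- ending at 20% or more above baseline (week 48, +25%): 48 − 12 = 36 weeks.

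Section 9.2.2.2.3 excludes none of the three.

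**Time between the two thresholds (assumed growth).** Where the 5 mm floor does not bind, the band spans a ratio 1.2B/1.2N = B/N. With growth by a factor g per 6 weeks, the time is 6 × ln(B/N)/ln(g). For g from 1.3 to 1.1 this is about 8 to 22 weeks at N = 0.7B and 16 to 44 weeks at N = 0.5B. The documents give no growth rate.

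**Number of patients.** Expected responders among 29 are 0.20 × 29 = 5.8 under the alternative and 0.05 × 29 = 1.45 under the null. Not all will relapse inside the band.

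**Timing.** A repeat scan on day 26 is about 4 weeks after the first, but not at least 4 weeks (28 days). It confirms PD under section 7.1.3 and not under section 7.1.3.3.1 or Table 8.

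**The case against.** The strongest reply is that the text can be read coherently. Section 7.1.3.3.2 makes irSD residual, so a scan that is PD from nadir cannot be SD. Relapse from irCR by a reappearing lesion is settled expressly. The note under Table 8 shows that continuing after confirmed irPD was foreseen. Confirmed PD is a listed stopping reason, and a reader would naturally let it override.

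Part of this stands. The residual reading removes the SD case and with it the whole band at N = 70% of baseline. But Table 8 defines irSD against baseline and contradicts that reading, which also leaves the irPR/irPD overlap for deeper responses. The irCR rule covers one route of relapse. The exception is discretionary, whereas the instruction in section 7.1.3 to continue is not. No general precedence is written.

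The objection on impact also stands. The primary ORR rests on a response already confirmed. The main PFS takes the first RECIST 1.1 PD whether or not drug is stopped. Duration of response is descriptive and is not among the objectives in section 3.2.

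The timing difference is minor. Most of the relevant passages set a minimum of 4 weeks, and section 7.1.3 itself points to irRECIST.

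**Conclusion.** The instructions conflict as written, and this is more than missing detail. The conflict covers max(1.2N, N + 5 mm) up to 1.2B, or only the irPR/irPD overlap (N at or below about 58% of B and N + 5 mm ≤ 0.7B) if irSD is read as residual. It should be corrected, but it does not threaten the trial's main conclusion.

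A reader might infer four stronger things that the documents do not support:

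- *Every relapsing responder is caught.* There is no conflict once the sum reaches 120% of baseline, nor for some very small sums (B = 10, N = 7 mm). The lower limit is not 1.2N throughout.
- *Section 7.1.3 is why the end of response is undefined.* That gap lies in section 9.2.2.2.3 and would remain if section 7.1.3 were repaired.
- *The primary result is at risk.* ORR and the RECIST 1.1 PFS are not affected. The effect on the stage 1 stable-disease provision is possible, not shown.
- *Response is prolonged by a known number of weeks.* Every figure in weeks depends on an assumed course or growth rate.

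I take irRC in section 9.2.2.2.1 to mean the criteria of section 7.1.3.3, whose heading carries that label.

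**What to change.** 1. In sections 9.2.2.2.1 (irRC-based PFS) and 9.2.2.2.3, state for endpoint scoring only that irPD is measured from nadir as in section 7.1.3.3.2, including the 5 mm minimum, and that a scan meeting both irPD and an irPR or irSD row is scored irPD. Give a scoring version of Table 8 with mutually exclusive rows.
2. In section 9.2.2.2.3, name the end event for response, its date (first or confirming scan) and the censoring rule.
3. For endpoint scoring, use one confirmation interval throughout.
4. The treatment instructions in sections 5.2.3, 5.8 and 7.1.3 and the notes under Table 8 contradict each other for these patients. The sponsor must reconcile them; no clinical rule is proposed here. The scoring rule belongs in section 9 because section 7.1.3 also uses irRECIST to decide discontinuation.

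The cost is wording only, with no extra scans or patients. Reported response durations may become shorter than under a baseline-referenced reading.
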